5. ADVERSE EVENTS

5.1. Adverse Events

At each evaluation, the investigator will determine whether any adverse events (AEs) have occurred. For the purpose of this protocol, an adverse event is any untoward medical occurrence, unintended disease or injury or untoward clinical signs (including laboratory findings) in subjects, users or other persons, whether or not related to the investigational medical device.

In this study, subjects should be encouraged to report AEs spontaneously or in response to general, non-directed questioning. If it is determined that an AE has occurred, the investigator should obtain all the information required to complete the AE Form of the CRF.

In addition, subjects will be instructed to contact the investigator, and/or study coordinator if any significant adverse events (e.g., MAE) occur between study evaluation visits.

Adverse event reporting begins when the index procedure is completed.

Adverse events should be followed to resolution or stabilization, and if an ongoing AE changes in severity, a new AE entry for this event should be recorded. If a mild adverse event changes to a moderate or severe adverse event, the end date for the mild event and the start date for the moderate or severe event should be the same. Additionally, the mild event is considered resolved with the initiation of the moderate or severe event.

Adverse events that are present at the end of a subject's participation in the study should be marked as on-going on the case report form and the subject should receive post-treatment follow-up as appropriate.

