3.2. Secondary Endpoints

The following endpoints will be also evaluated as secondary endpoints:

- Rate of Major Adverse Event (MAE) Rate in hospital and at 30 days, 1, 2 and 3 years post-procedure, defined as a composite rate of cardiovascular death, index limb amputation and ischemia-driven Target Lesion Revascularization (TLR).
- Rate of occurrence of arterial thrombosis of the treated segment.
- Rate of ipsilateral embolic events of the study limb.
- Rate of clinically-driven target lesion revascularization at 6, 12, 24 and 36 months.
- Patency rate at 12 months post-procedure, defined as freedom from clinically driven TLR and duplex ultrasonography restenosis (ultrasound peak systolic velocity ratio ≤ 2.4 or stenosis ≤50%)
- Rate of vascular access site complication defined as the combined rate of hematoma, AV fistula or a pseudoaneurysm that required intervention, such as surgical repair or transfusion, prolonged hospital stay or required a new hospital admission.
- Lesion success (per device), defined as achievement of a final in-lesion residual diameter stenosis of <50% (by QA), using any device after wire passage through the lesion. Pre- and post-dilatation of the lesion with a non-study device is considered part of assigned device treatment.
- Technical success (per device), defined as achievement of a final in-lesion residual diameter stenosis of <50% (by QA), using the CVT Everolimus-coated PTA Catheter without a device malfunction after wire passage through the lesion. Preand post-dilatation are considered part of assigned device treatment.
- Clinical success (per subject), defined as technical success without the occurrence of major adverse events during the procedure.
- Procedural success (per subject), defined as lesion success without the occurrence of major adverse events during procedure.
- Ankle-Brachial Index (ABI) changes before procedure compared with ABI at discharge and at 6 and 12 months.

Confidential Page 16 of 79

- Change in WIQ (walking impairment questionnaire) from pre-intervention at 6 and 12-months follow-up.
- Change in walking distance from pre-procedure at 6 and 12 months.
- Change in Rutherford classification grades of chronic limb ischemia from preintervention at 6 and 12-months follow-up for the treated limb.

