4.3. SFA PTA Procedure

Procedural Medications

During the procedure, subjects will receive appropriate anticoagulation and other therapy according to standard hospital practice. The use of any medication for the treatment of vessel spasm, subject agitation or discomfort, hypotension, arrhythmias and hemodynamic changes during the procedure is at the discretion of the investigator.

Baseline Angiography

The diagnostic and interventional procedure can be conducted via either contralateral or antegrade approach at the investigator's discretion. A pelvic angiogram (digital subtraction angiography, Magnetic Resonance (MR) angiography, or Computed Tomography (CT) angiography) with run-off must have been performed prior to the PTA procedure (run-off should include popliteal and distal vessels) to confirm patent inflow and outflow as well as run-off required within the inclusion criteria.

Treatment Strategy

This study allows for treatment of *de novo* occluded/stenotic or re-occluded/restenotic superficial femoral (SFA) or popliteal artery (P1 segment) lesions in a single limb that are \geq 3 cm (30 mm) and \leq 15 cm (150 mm) in cumulative length, with up to two (2) CVT Everolimus-coated PTA Catheters. The lesion(s) should be within 1 cm distal to the femoral bifurcation in the SFA and 3 cm from the proximal margin of the intercondylar fossa.

The timing and method of treatment of any contralateral non-target lesion(s) is at the discretion of the investigator; however, it should be >30 days before or after the study procedure. A contralateral non-target lesion(s) cannot be treated during the same procedure in order to avoid complications.

Subjects selected for treatment must have a patent inflow artery and outflow arteries free from significant lesions (\geq 50% stenosis) as confirmed by angiography. If the ipsilateral iliac artery is diseased, but not occluded, it may be treated prior to the treatment of the target SFA/popliteal lesion. Successful treatment of the inflow artery is defined as attainment of final residual diameter stenosis of <30% without residual dissection or complication during the treatment. Outflow arteries (distal popliteal, anterior or posterior tibial or peroneal arteries) with significant lesions (\geq 50% stenosis) may not be treated during the same procedure.

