Pre-dilatation will be performed for all target lesions with a non-study balloon catheter. After pre-dilatation, the investigator will determine the suitability of the lesion for treatment by PTA alone.

The target lesion should be treated after meeting the general and angiographic inclusion and exclusion criteria. Additional treatment modalities, including but not limited to, rotational or directional atherectomy, cryoplasty, scoring/cutting balloons, laser, brachytherapy or lithotripsy must not be performed in conjunction with this procedure.

The balloons should be sized to ensure the full length of the lesion is treated and that the balloon, upon inflation, apposes the arterial wall without oversizing.

Confidential Page 22 of 79

The initial inflation of the study device should be ≥ 1 minute.

For a residual stenosis >50% or significant dissection after study treatment, post-dilatation should be performed. A commercially available non-drug eluting nitinol stent may be used to treat a flow-limiting dissection or persistent residual stenosis if balloon inflation is unsuccessful. Post-dilatation of the stent, if required, should be done with the CVT Everolimus-coated PTA Catheter.

PTA Procedure

The appropriate balloon size will be selected after review of the subject's baseline angiogram and determination of the reference vessel diameter and lesion length.

Pre-dilatation will be performed on all subjects per the following sequence: after crossing of the target lesion with a guidewire, pre-dilatation will be performed with a non-study balloon catheter. Based on the suitability of the lesion, the investigator will determine if the lesion can be treated by PTA alone or if treatment with a stent is required (e.g. dissection, stenosis >50%). If a stent is required, the investigator will implant the stent and the patient cannot be included in the study (e.g. screen fail). If the lesion is suitable for PTA treatment alone, the CVT Everolimus- coated PTA Catheter will be used to treat the lesion.

All catheters, including the CVT Everolimus-coated PTA Catheter, should be delivered and deployed per their respective Instructions for Use (reference Appendix E for CVT Everolimus-coated PTA Catheter IFU). All balloon inflations and stent deployments, when applicable, should be captured per the angiographic core laboratory guidelines.

Criteria for Bail-Out or Alternative Procedures

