PROCEDURE/TEST	Prior to Procedure (Within 14 days)	Pre-Procedure (Within 24 hours)	PROCEDURE	Pre-Discharge	30 days (±7 days) Phone call or Office\hospital Visit	180 days (±30 days) Office/hospital visit	365 days (±30 days) Office /hospital visit	24 and 36 months (±30 days)
Patient Medical/Clinical History	√							
Chronic Concomitant Medications	✓			√	√	✓	✓	√
Patient Informed Consent	✓							
General/Inclusion Exclusion	√							
Angiographic/Anatomic Inclusion/Exclusion Criteria			✓					
Pregnancy Test (if applicable)	√							
Serum Hematology	✓			√ *				
Blood Chemistry	✓			√ *				
Peripheral Angiogram with Runoff		✓	✓					
Duplex Ultrasonography Examination	√ #			√		✓	✓	
Ankle Brachial Indices	✓			\checkmark		✓	✓	
Rutherford-Becker Classification	✓			✓		✓	✓	
WIQ	√					√	√	
Walking Test or Treadmill Test	✓					✓	✓	
Per-protocol Medications		√	✓	✓				
Adverse Events			√	√	✓	√	✓	✓

Confidential Page **27** of **79**

[#] optional * If the sub If the subject presents with less than desired clinical outcome or symptoms of an adverse event

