5.2. Anticipated Adverse Events

An anticipated adverse event is any untoward medical occurrence in a subject which is predefined in the protocol and/or Instruction for Use (IFU) and that is identified or worsens during a clinical study, regardless whether or not the event is considered related to the study device or drug regimen prescribed as part of the protocol.

The following is a list of adverse events that may result from the PTA procedure.

- Abrupt closure
- Acute MI
- Allergic reaction to contrast, concomitant medications (Allergic Reaction)
- Amputation
- Aneurysm
- Arrhythmias (bradycardia & tachycardia)
- Arterial dissection
- Arterial perforation or rupture
- Artery spasm
- AV fistula
- Bleeding

Confidential Page 28 of 79

- Bypass graft surgery (emergent or non-emergent)
- Chest pain
- Death (cardiovascular or non-cardiovascular related)
- Discomfort during the procedure
- Embolism/PTA catheter embolism
- Endocarditis
- Fever
- Groin Bruising/Discomfort
- Hematoma
- Hemorrhage
- Hypertension
- Hypotension
- Injury to the groin blood vessel
- Infection or pain at insertion site
- Ischemia
- Nausea
- Pseudoaneurysm
- Renal failure
- Restenosis
- Sepsis /infection
- Stroke/CVA
- Wound complication or wound infection
- Thrombosis
- Total occlusion
- Vomiting / nausea

The oral formulation of everolimus has been evaluated in clinical trials and is approved worldwide for the prophylaxis of organ rejection in adult kidney transplant recipients at low-moderate immunologic risk and for the treatment of patients with advanced renal cell carcinoma. Oral dose of everolimus depending on the indication ranges between 1.5 and 20 mg/day. The following list includes the known risks of everolimus at these oral doses. The following is a list of theoretical adverse events that may result from the addition of everolimus to a PTA catheter:

- Abdominal pain
- Anemia
- Angioedema
- Anorexia
- Asthenia
- Constipation

Confidential Page 29 of 79

- Cough
- Delayed wound healing/fluid accumulation
- Diarrhea
- Dyslipidemia (including hyperlipidemia and hypercholesterolemia)
- Dyspnea
- Dysgeusia
- Dyspepsia
- Dysuria
- Dry skin
- Edema (peripheral)
- Epistaxis
- Fatigue
- Headache
- Hematuria
- Hyperglycemia
- Hyperlipidemia
- Hyperkalemia
- Hypertension
- Hypokalemia
- Hypomagnesemia
- Hypophosphatemia
- Increased serum creatinine
- Infections and serious infections: bacterial, viral, fungal, and protozoal infections
- Insomnia

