5.3. Adverse Event Severity

The investigator will use the following definitions to rate the severity of each adverse event:

Mild	Awareness of a sign or symptom that does not interfere with the subject's usual activity or is transient, resolved without treatment and with no sequelae
Moderate	Interferes with the subject's usual activity and/or requires symptomatic treatment
Severe	Symptom(s) causing severe discomfort and significant impact of the subject's usual activity and requires treatment

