6.2. Analysis Populations

The primary endpoints will be analyzed on the entire safety population and on the evaluable subject population, as appropriate.

The safety population will consist of all subjects who enrolled into the study and for whom the procedure had been initiated.

All effectiveness endpoints will be analyzed using the evaluable population, which consists of subjects who had no bailout procedure and at least one valid follow-up visit.

Confidential Page 34 of 79

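### Section 5.1 starts adverse-event reporting at completion of the index procedure, but Table 2 and Appendix F schedule it during the procedure; read as an onset cutoff, 5.1 would leave non-serious on-table events off the AE form

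*Combined protocol and SAP*

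**What the plan says.** Section 5.1 contains the only sentence that sets a start for general adverse-event reporting: "Adverse event reporting begins when the index procedure is completed". The same section asks the investigator, at each evaluation, whether events have occurred, and sends them to the AE form of the case report form.

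Table 2 (end of section 4.6) and Appendix F each have a row headed "Adverse Events". In both, the two pre-procedure columns are empty and the first tick stands under the procedure.

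Other sections deal with events on the table:

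- Section 5.2 includes "Discomfort during the procedure" in its list of anticipated events from the PTA procedure.
- Section 4.3 leaves to the investigator the use of medication for "treatment of vessel spasm, subject agitation or discomfort, hypotension, arrhythmias and hemodynamic changes during the procedure".
- Section 5.3 grades an event as Moderate if, among other grounds, it "requires symptomatic treatment".

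On sequence, section 4.3 states: "Pre-dilatation will be performed for all target lesions with a non-study balloon catheter". Section 3.2, in defining lesion success, states: "Pre- and post-dilatation of the lesion with a non-study device is considered part of assigned device treatment".

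**The concern.** A start rule for adverse events is normally read as a rule about onset: events that begin before the stated time are not study adverse events. On that reading, 5.1 excludes the interval in which the balloon is inflated and the drug delivered, while the schedule of events includes it.

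What is at stake is the record of acute, non-serious events. A site that applies 5.1 literally would not enter a treated hypotensive episode or a mild contrast reaction during the procedure; a site that works from Table 2 would. With up to eight sites, the acute adverse-event profile could differ between sites for reasons unrelated to the device. Section 9.6 calls this a first-in-human study, and safety is part of the stated objective, so acute tolerability is something readers will look for.

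**Working it through.** No arithmetic applies. The plan gives no figure on this point, and the question does not depend on alpha, power, event rates or sample size. The check sets the texts side by side.

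**1. Start time in each place.**

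| Place | Start of adverse-event collection |
|---|---|
| Section 5.1 | Completion of the index procedure |
| Table 2 | First tick in column 3 of 8 (procedure); columns 1 and 2 empty; columns 3 to 8 ticked, 6 ticks in all |
| Appendix F | Same layout as Table 2 |
| Section 9.8, Table 3, adverse-event row | Ongoing; no start given |
| Section 5.6, serious events | Reporting deadlines only; no start given |

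Table 3 and section 5.6 do not settle the matter. The disagreement is between 5.1 and the two schedules.

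**2. Does the protocol contemplate events in the disputed interval?** Yes. One anticipated event in 5.2 is defined by occurring during the procedure, so it could never be recorded under an onset cutoff at completion. Section 4.3 provides for drug treatment of spasm, discomfort, hypotension and arrhythmia on the table. Any of these that needs symptomatic treatment meets one of the grounds for Moderate in 5.3, so such events are not all trivial.

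**3. Which events have another route?**

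- Serious events related to the device or procedure: section 5.6 and the serious-event row of Table 3.
- Deaths: all are reviewed by the Clinical Events Committee (section 10.4).
- Complications visible on angiography: filming under Appendix M, with the procedure log or worksheet uploaded; arterial flow grading under Appendix B.
- All adverse events, in general terms: Appendix H, item 15, requires the investigator to inform the sponsor.
- Reactions that lead to discontinuation: documented under section 3.8.
- An in-hospital summary form is named in Table 3, but the forms in Appendix L are not reproduced, so its content is unknown.

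What remains is non-serious hypotension, arrhythmia, contrast reaction or discomfort during the procedure. Angiography does not show these. Their capture rests on the AE form, on the general duty in Appendix H, or on forms that cannot be seen.

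**4. Where should the interval begin?** Section 3.7 completes enrollment when the study catheter enters the vasculature. Pre-dilatation comes before that in all subjects (4.3), and the success definitions in 3.2 count it as part of the assigned treatment. A start at catheter entry would agree with a tick in the procedure column but would leave out a step that the protocol treats as part of the intervention.

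**The case against.** The strongest reply is that 5.1 speaks of reporting, not of onset. It may mean only that forms are opened once the procedure ends and then take in whatever happened during it. That reading fits the backward-looking question at each evaluation in 5.1, the pre-discharge documentation in 4.5, both schedules and Appendix H. It is the more coherent reading of the whole protocol. This stands as a possibility, and divergence between sites is a risk rather than something shown. But nothing in the text selects that reading, and a site that takes the sentence at its word is not departing from the protocol.

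It is also fair that the case report forms might already settle the point. They might, but they cannot be assumed to, and the sentence in 5.1 would still disagree with the schedule.

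Third, section 6.4 plans no tabulation of non-serious adverse events, so no pre-specified result changes. That stands and limits the severity.

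A reader might infer more than the documents support:

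- *That the primary or success endpoints are affected.* The primary safety endpoint counts cardiovascular death, index limb amputation and ischemia-driven revascularization at 6 months; non-serious on-table events are not among them. Clinical and procedural success, and the peripheral embolization definition in Appendix B, carry their own wording for events during the procedure.
- *That 5.1 contradicts the safety population.* Section 6.2 takes enrolled subjects "for whom the procedure had been initiated". That fixes who is counted, not which events are collected, and the two can differ without contradiction.
- *That serious events are lost.* Section 5.5 defines a serious event as a kind of adverse event, so a literal cutoff could in principle reach them, but related ones have the separate route in 5.6.
- *That the loss can be sized by comparing the anticipated-event list with the complications named for filming.* Overlap between lists does not measure under-recording, and the filming list is given only as examples.

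**Conclusion.** The point holds as an internal inconsistency: section 5.1 is wrong as written against Table 2 and Appendix F, and it sits badly with an anticipated event in 5.2 that can only occur during the procedure. The consequence is conditional. If a site reads 5.1 as an onset cutoff, non-serious on-table events are left off its AE form, and the acute record may not be comparable between sites.

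The size of any loss cannot be estimated, because the documents give neither an on-table event rate nor the case report forms. No effect on the primary or any other pre-specified endpoint is claimed. The conclusion assumes that no form or completion instruction outside these documents already fixes the onset time; if one does, what remains is a wording error. Severity is minor to moderate.

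**What to change.** Replace the sentence in 5.1 so that it agrees with Table 2 and Appendix F, for example: *In every enrolled subject, all adverse events with onset from the start of the index procedure, including pre-dilatation with the non-study balloon, are recorded on the AE form.* If the case report form completion instruction says otherwise, align it.

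The wording covers events before the study catheter enters, but only in subjects who go on to be enrolled; subjects who receive a stent after pre-dilatation remain screen failures under 4.3. Section 3.5 already requires consent before any investigation-related procedure, so no consent step is added.

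The cost is one sentence and at most one form instruction, with no new visit or test. The downside is possibly a few more AE entries and a slightly less favourable acute profile. If the sponsor intended the milder reading all along, the sentence only makes that explicit.

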5.2. Anticipated Adverse Events

An anticipated adverse event is any untoward medical occurrence in a subject which is predefined in the protocol and/or Instruction for Use (IFU) and that is identified or worsens during a clinical study, regardless whether or not the event is considered related to the study device or drug regimen prescribed as part of the protocol.

The following is a list of adverse events that may result from the PTA procedure.

- Abrupt closure
- Acute MI
- Allergic reaction to contrast, concomitant medications (Allergic Reaction)
- Amputation
- Aneurysm
- Arrhythmias (bradycardia & tachycardia)
- Arterial dissection
- Arterial perforation or rupture
- Artery spasm
- AV fistula
- Bleeding

Confidential Page 28 of 79

- Bypass graft surgery (emergent or non-emergent)
- Chest pain
- Death (cardiovascular or non-cardiovascular related)
- Discomfort during the procedure
- Embolism/PTA catheter embolism
- Endocarditis
- Fever
- Groin Bruising/Discomfort
- Hematoma
- Hemorrhage
- Hypertension
- Hypotension
- Injury to the groin blood vessel
- Infection or pain at insertion site
- Ischemia
- Nausea
- Pseudoaneurysm
- Renal failure
- Restenosis
- Sepsis /infection
- Stroke/CVA
- Wound complication or wound infection
- Thrombosis
- Total occlusion
- Vomiting / nausea

The oral formulation of everolimus has been evaluated in clinical trials and is approved worldwide for the prophylaxis of organ rejection in adult kidney transplant recipients at low-moderate immunologic risk and for the treatment of patients with advanced renal cell carcinoma. Oral dose of everolimus depending on the indication ranges between 1.5 and 20 mg/day. The following list includes the known risks of everolimus at these oral doses. The following is a list of theoretical adverse events that may result from the addition of everolimus to a PTA catheter:

- Abdominal pain
- Anemia
- Angioedema
- Anorexia
- Asthenia
- Constipation

Confidential Page 29 of 79

- Cough
- Delayed wound healing/fluid accumulation
- Diarrhea
- Dyslipidemia (including hyperlipidemia and hypercholesterolemia)
- Dyspnea
- Dysgeusia
- Dyspepsia
- Dysuria
- Dry skin
- Edema (peripheral)
- Epistaxis
- Fatigue
- Headache
- Hematuria
- Hyperglycemia
- Hyperlipidemia
- Hyperkalemia
- Hypertension
- Hypokalemia
- Hypomagnesemia
- Hypophosphatemia
- Increased serum creatinine
- Infections and serious infections: bacterial, viral, fungal, and protozoal infections
- Insomnia
- Interaction with strong inhibitors and inducers of CYP3A4 or PgP
- Leukopenia
- Lymphoma and other malignancies (including skin cancer)
- Male infertility
- Mucosal inflammation (including oral ulceration and oral mucositis)
- Nausea
- Neutropenia
- Non-infectious pneumonitis
- Pain: extremity, incision site and procedural, and back
- Proteinuria
- Pruritus
- Pyrexia
- Rash
- Stomatitis

Confidential Page 30 of 79

- Thrombocytopenia
- Thrombotic microangiopathy
- Thrombotic thrombocytopenic purpura
- Tremor
- Urinary tract infection
- Upper respiratory tract infection
- Vomiting

